### Therapy Delays

Therapy delays are only defined for avelumab administration and are defined as infusions given ≥3 days from the planned administration date. Delays are only defined for subjects who receive at least two administrations of avelumab and will be derived based on the time between two administrations:

Therapy Delay =  $[date\ of\ current\ administration] - [date\ of\ previous\ administration] - 14$ 

Delays will be grouped into the following categories:

- No delay (including delay of 1-2 days)
- Delay of 3-6 days
- Delay of 7-13 days
- Delay of 14-20 days
- Delay of ≥21 days

The number and percentage of subjects with delayed avelumab administration and the longest observed delay (days) per subject will be summarized by cohort dose level. If possible, the number and percentage of subjects with therapy delays attributable to the COVID-19 pandemic will also be presented.

### Therapy Interruptions

A therapy interruption is defined as omission of a full cycle of a planned study intervention. Therapy interruptions are only defined if the intervention is later restarted.

Avelumab: A therapy delay of greater than 13 days is considered a therapy interruption.

M3814 (Parts A and FE only): fourteen consecutive days of missed M3814 is considered a therapy interruption.

The number and percentage of subjects with an interruption in study drug administration and the longest observed interruption (cycles) per subject will be summarized by cohort dose level. If possible, the number and percentage of subjects with therapy interruptions attributable to the COVID-19 pandemic will also be presented.

# 14 Efficacy Analyses

# 14.1 Best Overall Response

Analysis sets: FAS

The confirmed Best Overall Response (BOR) is defined as the best confirmed response obtained among all tumor assessments after the start of study intervention until documented disease progression or start of subsequent anti-cancer treatment, taking requirements for confirmation into account as detailed below. Confirmed BOR will be evaluated according to the Response Evaluation Criteria in Solid Tumors (RECIST) v1.1 based on the Investigator's assessment of disease.

Only tumor assessments performed on or before the start of any further anti-cancer treatment will be considered in the assessment of BOR. Clinical deterioration will not be considered as documented disease progression. If a tumor assessment was performed on the same day as start of

new anti-cancer therapy, it will be assumed that the tumor assessment was performed prior to the start of the new anti-cancer therapy, therefore the tumor assessment will be included in the assessment of BOR.

Table 6 summarizes the derivation rules described by Eisenhauer, et al. for the BOR when confirmation from subsequent assessment is needed. For subjects who have non-target lesions only at baseline, the time-point tumor assessment of "Non-CR/non-PD" will be evaluated with the same criteria as SD (minimum criteria for SD duration) in deriving the overall BOR.

Table 6: Best Overall Response When Confirmation of CR/PR Is Required

Overall response 1st time point	Overall response subsequent time point	Best overall response (BOR)
CR	CR	CR
CR	PR	SD, PD or PR a
CR	SD	SD provided minimum criteria for SD duration met; otherwise, PD
CR	PD	SD provided minimum criteria for SD duration met; otherwise, PD
CR	NE	SD provided minimum criteria for SD duration met, otherwise NE
PR	CR	PR
PR	PR	PR
PR	SD	SD
PR	PD	SD provided minimum criteria for SD duration met, otherwise, PD
PR	NE	SD provided minimum criteria for SD duration met, otherwise NE
NE	NE	NE

CR = complete response, PR = partial response, SD = stable disease, PD = progressive disease, NE = not evaluable.

\* If a CR is truly met at first time point, then any disease seen at a subsequent time point, even disease meeting PR criteria relative to baseline, makes the disease PD at that point (since disease must have reappeared after CR). Best response would depend on whether minimum duration for SD was met. However, sometimes 'CR' may be claimed when subsequent scans suggest small lesions were likely still present and in fact the patient had PR, not CR at the first time point. Under these circumstances, the original CR should be changed to PR and the best response is PR.

## BOR based on confirmed responses:

- CR = at least two determinations of CR at least 4 weeks apart (with no PD in between)
- PR = at least two determinations of PR or better (PR followed by PR or PR followed by CR) at least 4 weeks apart (and not qualifying for a CR), with no PD in between
- SD (applicable only to participant with measurable disease at baseline) = at least one SD assessment (or better) ≥ 8 weeks after start date (and not qualifying for CR or PR).
- Non-CR/non-PD (applicable only to participants with non-measurable disease at baseline)
   at least one non-CR/non-PD assessment (or better) ≥ 8 weeks after start date (and not qualifying for CR or PR).

- PD = PD ≤ 16 weeks after start date (and not qualifying for CR, PR, non-CR/non-PD or SD).
- Not Evaluable (NE): all other cases.

SD can follow PR only in the rare case that tumor increases by less than 20% from the nadir, but enough that a previously documented 30% decrease from baseline no longer holds. If this occurs the sequence PR-SD-PR is considered a confirmed PR. A sequence of PR – SD – SD – PD would be a best response of SD if the minimum duration for SD definition has been met.

Objective Response (OR) is defined as a confirmed BOR of complete response (CR) or partial response (PR) according to RECIST v1.1.

The number and percentage of subjects with BOR of CR, PR, SD, PD, non-CR/non-PD (applicable only to subjects with non-measurable disease at baseline), and NE will be tabulated. Subjects with BOR of NE will be summarized by reason for having NE status. The following reasons will be used:

- No Baseline Assessment
- No post-baseline assessments due to death within 8 weeks after treatment start
- No post-baseline assessments due to other reasons
- All post-baseline assessments have overall response NE
- New anti-cancer therapy started before first post-baseline assessment
- SD of insufficient duration (<6 weeks after treatment start without further evaluable tumor assessment)
- PD too late (i.e., tumor assessment of PD was >16 weeks after treatment start and there
  was no tumor assessment in between)

Special and rare cases where BOR is NE due to both early SD and late PD will be classified as 'SD too early'.

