Dipstick Urinalysis	х	x		x			Perform at Visit 6 (Week 8) and then Q8W	x				Full urinalysis (dipstick + microscopic analysis) should be performed only at Screening and EoT. If dipstick urinalysis at other assessments is abnormal, full analysis should be performed. See Appendix 6.
Free T4, TSH	X	X				Х	Q6W		X			

		Treat	ment l	Perio	d: M3	3814+	avelumab	End	of Trea	tment	(EoT)/FU	Notes
Study Period	Screening	DL	T Peri	od				EoT	EoT Safety FU		Long-term FU	
Visit	-1	1	2	3	4	5	n				Q12W	During on-treatment period, after Day 29, visits
								(Within				will be every 2 wks on days of avelumab infusions until EoT.
Study Day (± Visit window)	-28 to -1	1	15 (± 1)	22 (± 1)	29 (± 1)		n + 14 d (± 2)	7 days of		90 d (± 5)	(± 7)	All participants discontinuing study interventions for any reason must undergo EoT Visit within 7 days after decision to discontinue study interventions, but (if possible) before any new antineoplastic therapy is started.
								nue)				The safety follow-up period will be 30 days (± 5 days) and 90 days (± 5 days) after the last dose of avelumab, see Section 4.1.1.3.
M3814		Cont	inuou	s BID	dosi	ing (7	days/wk)					See Section 6.6.5.1 for details.
Premedication (avelumab)		x	x		x	X						Required only for first 4 avelumab infusions, as needed thereafter. See Section 6.5.5.
Avelumab		x	x		x	x	x					800 mg iv Q2W until PD. For post-PD treatment, see Section 6.6.6. For post-CR treatment, see Section 4.1.1.2.
12-Lead ECG (including QTcF)	х	x	x	x				x				PK-matched digital 12-lead resting ECG will be performed in triplicate at predose,1, 2 and 6 h post-M3814 administration before blood collection for PK, CCI sampling, followed by vital signs after the morning dose only. The assessment should be performed after the participant has been in supine position breathing quietly for ≥ 5 min at predose and all postdose sampling times.
Tumor Assessment (RECIST v 1.1)	х						Day 56, Day 112, Day 168, then Q12W	x	x		x	Tumor imaging by CT or MRI at Baseline to document tumor lesion burden. Can be up to 28 days prior to first study intervention. Then at D56, D112, D168 and then Q12W, until confirmed PD, the start of subsequent systemic anticancer therapy, or the end of the study. At EoT/Long-term FU, tumor response assessment is only required if participant has not progressed or has not started a new treatment.

		Treat	ment l	Perio	d: M3	814+	avelumab	End	of Trea	tment	(EoT)/FU	Notes
Study Period	Screening	DL	T Peri	od				EoT	Safet	Safety FU Long-term FU		

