#### Definition of duration

Duration will be calculated by the difference of start and stop date + 1. For example, AE duration (days) = AE end date - AE start date + 1

Unless otherwise specified, the time since an event will be calculated as reference date minus date of event. For example, time since last dose date will be calculated as the event date – the date of last dose.

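### SAP 14.1 gives two different minimum times for stable disease (8 weeks and 6 weeks), and the 8-week one falls exactly on the first scheduled scan at Day 56

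*SAP*

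**What the plan says.** SAP 14.1 defines a BOR of SD as "at least one SD assessment (or better) ≥ 8 weeks after start date (and not qualifying for CR or PR") and uses the same limit for participants with non-measurable disease: "at least one non-CR/non-PD assessment (or better) ≥ 8 weeks after start date". PD counts as BOR only up to 16 weeks after start, and every remaining case is NE.

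The same section then lists the reasons under which NE participants are tabulated. One is "SD of insufficient duration (<6 weeks after treatment start", with no further evaluable assessment. A closing rule says that cases where "BOR is NE due to both early SD and late PD will be classified as" SD too early.

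Table 6 in SAP 14.1 depends on the minimum but gives no number, for example "SD provided minimum criteria for SD duration met; otherwise, PD". The footnote to its CR-then-PR row does the same: "Best response would depend on whether minimum duration for SD was met".

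On timing, Tables 1 and 4 of Protocol section 1.3 (Parts A and FE) schedule tumor imaging "Then at D56, D112, D168 and then Q12W, until confirmed PD", and Table 3 gives the same days for Part B. SAP 9.1 numbers the first treatment day as Day 1 with no Day 0. It says "Duration will be calculated by the difference of start and stop date + 1", but computes time since an event as a plain difference of dates.

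**The concern.** One section carries two limits for the same thing, 14 days apart, and nothing elsewhere in either document reconciles them. Table 6 inherits the problem.

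The stricter limit also leaves no room around the first scan. A scan one day early fails, and whether an on-time scan passes depends on a day count that SAP 14.1 does not state. SAP 9.3 (Tumor assessments) makes early dates more likely: an evaluation spread over several days takes its earliest scan date, and one with no day recorded takes the 1st of the month.

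Confirmed BOR is a secondary endpoint in every part and is tabulated by category in small dose levels. The interim efficacy analysis in SAP 6.1 is timed to the Day 112 scan, when BOR rests on the first two scans; the SAP does not say which outputs it will include.

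**Working it through.** The plan has no calculated figure to reproduce here. The check is day arithmetic on its stated limits.

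**Inputs.** Limits of 8, 6 and 16 weeks (SAP 14.1); scans at Days 56 and 112 (Protocol 1.3); Day 1 = first treatment day and the two day-count rules (SAP 9.1); cohort and part sizes (Protocol 6.6.2 and 6.6.4).

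**Limits in days.** 8 × 7 = 56; 6 × 7 = 42; 16 × 7 = 112. The two SD limits differ by 56 − 42 = 14 days.

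**Elapsed time at Study Day D.** Plain difference = D − 1; difference plus 1 = D.

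| SD scan on | Plain difference | 8 weeks met? | Plus 1 | 8 weeks met? |
|---|---|---|---|---|
| Day 55 | 54 d (7.71 wk) | no | 55 d (7.86 wk) | no |
| Day 56 | 55 d (7.86 wk) | no | 56 d (8.00 wk) | yes |
| Day 57 | 56 d (8.00 wk) | yes | 57 d (8.14 wk) | yes |

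**Gap in the NE reasons.** A last evaluable SD on Days 42 to 55 (plus 1) or Days 43 to 56 (plain) is too early for SD yet not below 6 weeks. If nothing evaluable follows, it is NE and no listed reason describes it.

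**Effect on BOR**, assuming no other evaluable scan between the two shown:

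| Sequence | 8 weeks, plus 1 | 8 weeks, plain | 6 weeks, either count |
|---|---|---|---|
| SD Day 56, PD Day 112 | SD | PD | SD |
| SD Day 55, PD Day 112 | PD | PD | SD |
| SD Day 55, PD Day 113 | NE | PD | SD |

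The last row turns on the 16-week PD limit: Day 113 is 113 days with plus 1 (16.14 weeks, too late) and 112 days by plain difference (16.00 weeks, within the limit). An unconfirmed PR on Day 55 followed by PD on Day 112 also becomes PD under the 8-week rule.

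**Scan window.** No window is stated for scans. If the ±2 days of the on-treatment visit column applied (an assumption), the range would be Days 54 to 58. Days 54 and 55 would fail with plus 1, and Days 54, 55 and 56 by plain difference.

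**Table 6.** Six of 11 rows use the minimum: CR-SD, CR-PD, CR-NE, PR-PD and PR-NE in their text, and CR-PR through the footnote.

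**Size of one reclassification.**

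- Dose level of 3 to 6: 1/6 = 16.7 to 1/3 = 33.3 percentage points.
- Part A overall (6 to 30): 1/30 = 3.3 to 1/6 = 16.7.
- Part B overall (6 to 24): 1/24 = 4.2 to 16.7.
- Part FE overall (6 to 12): 1/12 = 8.3 to 16.7.

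**The case against.** - **The 6-week text only labels.** The two definitions both say 8 weeks and they set the category; the 6-week figure applies after a participant is already NE. This is largely right: a programmer who follows the definitions gets one category once the day count is fixed. The unlabelled gap remains, and so does the Day 55 problem, which comes from the definitions themselves.
- **The day count is open.** The definitions speak of time after the start date, which could follow the plain-difference rule in SAP 9.1. This stands as a caution: two of the three sequences above change with the count. Plus 1 seems the more natural reading, because Table 6 and the NE reason call the quantity a duration. Either way, Day 55 fails.
- **The scan may fall on Day 57.** Protocol 8.1.1.2 counts post-treatment scans every 8 weeks from Day 1, and SAP Tables 2 and 3 put Visit 6 on Day 57. But those SAP tables cover laboratory, vital-sign and ECG data, and all three schedules of activities say Day 56 for imaging.
- **Other scans can rescue the category.** Scans at end of treatment, at the 30-day follow-up, or after discontinuation may show SD past 8 weeks. This is true. In the CR-SD row, an on-schedule second scan meets the minimum by itself. So six of 11 rows shows how widely the minimum is used, not how many participants are affected.
- **The stakes are low.** Protocol 9.4.1 defines the BOR rate as confirmed CR or PR, no disease-control rate is derived, and no hypothesis is tested. This is accepted, and it limits the weight of the point. The percentage shifts are what any single participant contributes in cohorts this small.

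**Conclusion.** The concern holds. SAP 14.1 contradicts itself on the minimum time for SD, and its 8-week limit falls on the first planned scan with no tolerance and no stated day count. A participant whose only SD-or-better assessment is a first scan one day early is reported as PD or NE. Anyone still SD at Day 112 keeps SD.

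The effect is confined to the descriptive SD, non-CR/non-PD, PD and NE counts and the NE-reason table. Confirmed CR and PR, ORR, DOR, PFS and OS are untouched. One case moves a dose-level category by 17 to 33 points. The documents do not say how often first scans are early, so no expected number of cases can be given. The SAP should be corrected, but the point does not threaten the primary objectives.

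**What to change.** State one minimum, with its day count, in the SD and non-CR/non-PD definitions, in Table 6 and in the NE reasons.

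- **Preferred: 6 weeks**, defined as assessment date − treatment start date + 1 ≥ 42 days. This agrees with the existing NE reason, uses the same plus-1 count from treatment start as the PFS and OS formulas, and clears Day 56 by 14 days. Its downside is that an unscheduled SD scan at 6 to under 8 weeks would also count as SD.
- **If 8 weeks is kept:** change the NE reason to under 8 weeks and add an explicit allowance for an early first scan. Changing the label alone would leave the Day 55 participant as PD or NE.

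In either case, state the same day count for the 16-week PD limit. The cost is SAP wording only, with no new data, and it should be settled before results are seen.

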#### Objective Response

The confirmed objective response rate (ORR) is defined as the proportion of subjects having reached a confirmed BOR of CR or PR according to RECIST v1.1, as evaluated by the Investigator. Subjects with BOR of non-CR/non-PD are not considered to have achieved objective response. Subjects who do not have a post-baseline radiographic tumor assessment due to early progression; who receive anti-cancer treatments other than the study intervention prior to reaching a CR or PR; or who die, progress, or drop out for any reason prior to reaching a CR or PR will be counted as non-responders in the assessment of ORR.

ORR will be tabulated by cohort dose level along with the two-sided 95% CI using the Clopper-Pearson method (exact CI for a binomial proportion as computed by default by the SAS FREQ procedure using the EXACT option).

# 14.2 Duration of Response

Analysis sets: FAS

Duration of Response (DOR) is defined only for subjects with an OR. DOR is calculated as the time from first documentation of OR (CR or PR according to RECIST 1.1, as evaluated by the Investigator) to the date of first documentation of objective progression of disease or death due to any cause. For subjects with an OR but neither documented disease progression nor death as of the cut-off date for the analysis, DOR will be censored at the date of the last adequate tumor assessment. The censoring rules for DOR are the same as those described for progression-free survival (PFS) in Section 14.4.

DOR (months) = (date of PD or death – date of  $1^{st}$  objective response + 1)/30.4375

Kaplan-Meier (i.e., product-limit) estimates of median DOR time will be presented by cohort dose level together with two-sided 95% CIs calculated according to Brookmeyer and Crowley (3). The number of subjects at risk (i.e., with ongoing response) vs. failed along with Kaplan-Meier estimates of ongoing response probability at 3, 6, and 12 months will be estimated with corresponding two-sided 95% CIs derived using the log-log transformation according to Kalbfleisch and Prentice (4) (i.e., CONFTYPE=loglog default option in SAS LIFETEST procedure). The estimate of the standard error will be computed using Greenwood's formula.

If the number of subjects with OR is small, the Kaplan-Meier method may not provide reliable estimates. In this case, only descriptive statistics or listings will be provided.

# 14.3 Tumor Shrinkage

Analysis sets: FAS

Tumor shrinkage is defined only for subjects with both a baseline and post-baseline tumor assessment and is derived as the percent change from baseline in target lesions (sum of longest diameter for non-nodal lesions and short axis for nodal lesions) at each time point. See Section 9.1 for the definition of baseline and percent change from baseline.

The percent change from baseline in target lesions as well as the first occurrence of a new lesion and subject off treatment will be displayed against time point (weeks) in a line/spider plot. The lines of the plot will be color coded according to cohort dose level.

The maximum percent reduction in target lesions from baseline will be identified across all the post-baseline assessments until documented PD or start of subsequent anti-cancer treatment. The maximum percent reduction is equivalent to the smallest percent change from baseline.

A waterfall plot of the maximum percent reduction in target lesions from baseline will also be created. Bars in the waterfall plot will be color coded according to cohort dose level.

For Part B, a listing with details of the irradiated lesions will be provided.

# 14.4 Progression Free Survival

Analysis sets: FAS

Progression free survival (PFS) time is defined as the time (in months) from treatment day 1 until the date of the first documentation of objective PD per RECIST v1.1 as determined by the Investigator or death due to any cause, whichever occurs first.

PFS time (months) = (Date of event or censoring – Treatment start date + 1)/ 30.4375

If a tumor assessment was performed on the same day as start of new anti-cancer therapy, it will be assumed that the tumor assessment was performed prior to the start of the new anti-cancer therapy, therefore, the tumor assessment will be included in the derivation of the PFS time.

An adequate tumor assessment is defined as a result that is not "NE" or "NA" (Not Applicable).

The censoring and event date options for the PFS and DOR analyses are presented in Table 7.

Table 7: Outcome and Event Dates for PFS and DOR Analyses

Scenario	Date of event / censoring	Outcome
No adequate baseline assessment	Treatment day 1	Censored a
If the last tumor assessment is beyond 6 months from the first dose:  Progression or death ≤ 24 weeks after last tumor assessment	Date of progression or death	Event
If the last tumor assessment is within 6 months from the first dose: Progression or death $\leq$ 16 weeks after last tumor assessment or $\leq$ 16 weeks after treatment day 1	Date of progression or death	Event
If the last tumor assessment is beyond 6 months from the first dose:  Progression or death > 24 weeks after last tumor assessment	Date of last evaluable assessment	Censored
If the last tumor assessment is within 6 months from the first dose:  Progression or death > 16 weeks after last tumor assessment	Date of last evaluable assessment	Censored
No progression	Date of last evaluable assessment	Censored
Treatment discontinuation due to 'Disease progression' without documented progression	Not applicable.	Information is ignored. Outcome is derived based on documented progression only.
New anti-cancer therapy given	Date of last evaluable tumor assessment before anti-cancer therapy is given	Censored

a However if the subject dies ≤ 16 weeks after treatment day 1, the death is considered an event with date on death date.

PFS will be summarized for the FAS by dose level using the Kaplan-Meier method and displayed graphically when appropriate. Median event times and two-sided 95% CIs for each median will be provided.

The PFS time or censoring time and the reasons for censoring will also be presented in a subject listing.

Frequency (number and percentage) of subjects with each event type (PD or death) and censoring reasons will be presented by treatment group. Reasons for censoring will be summarized according to the categories in Table 8 following the hierarchy shown.

Table 8: PFS Censoring Reasons and Hierarchy

Hierarchy	Condition	Censoring Reason
1	No adequate baseline assessment	No adequate baseline assessment
2	Start of new anti-cancer therapy before event	Start of new anti-cancer therapy
3	Event more than 16 (or 24 if beyond 6 months from the first dose of study treatment) weeks after last adequate post-baseline tumor assessment / date of first dose of study treatment (see also Table 7)	Event after missing assessments a
4	No event and [withdrawal of consent date ≥ date of first dose of study treatment OR end of study (EOS) = subject refused further FU]	Withdrawal of consent
5	No event and lost to follow-up in any disposition eCRF page	Lost to follow-up
6	No event and EOS present and no adequate post-baseline tumor assessment	No adequate post-baseline tumor assessment
7	No event and none of the conditions in the prior hierarchy are met	Ongoing without an event

<sup>a More than 16 (or 24) weeks after last adequate tumor assessment (see also Table 7)

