	RT Short-term Safety FU	RT Mid-term Safety FU	RT Long-term Safety FU	Avelumab Treatment	EoT	30-Day Safety FU	90-Day Safety FU	Long- term FU	If participant discontinues avelumab prior to RT Long-term Safety FU, RT Long-term Safety FU can be performed by telephone.
Study Day (± Visit window)	43 (± 7)	99 (± 7)	351 (± 2)	n+14 d (± 2)	(Within 7 days of decision to discontinue)	30 days (± 5)	90 days (± 5)	(Q12W)	During on-treatment period, after Day 29, visits will be every 2 wks on days of avelumab infusions until EoT. All participants discontinuing study interventions for any reason must undergo an EoT Visit within 7 days after decision to discontinue study interventions, but (if possible) before any new antineoplastic therapy is started. The safety follow-up period will be 30 days (± 5 days) and 90 days (± 5 days) after the last dose of avelumab, see Section 4.1.1.3.
Premedication avelumab	x								Required only for first 4 avelumab infusions, as needed thereafter. See Section 6.5.5.
Avelumab	x	x	x	x					800 mg iv Q2W until PD. For post-PD treatment, see Section 6.6.6. For post-CR treatment, see Section 4.1.1.2.
Free T4, TSH	X			Q6W		X			Q6W until PD.
12-Lead ECG					X				
Tumor assessment (RECIST v 1.1)				Day 56, Day 112, Day 168, then Q12W	x	x		X	At D56, D112, D168 and then Q12W, until confirmed PD, the start of subsequent systemic anticancer therapy, or the end of the study. At EoT/Long-term FU, tumor response assessment is only required if participant has not progressed or has not started a new treatment.

Study Period	RT Safe	ty FU Visits	and Avelumab T	reatment	End o	of Treatme	nt (EoT)/FU	I	Notes
	RT Short-term Safety FU	RT Mid-term Safety FU	RT Long-term Safety FU	Avelumab Treatment	EoT	30-Day Safety FU	90-Day Safety FU	Long- term FU	If participant discontinues avelumab prior to RT Long-term Safety FU, RT Long-term Safety FU can be performed by telephone.

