8.1.1 Clinical Assessments

8.1.1.1 Tumor Response Assessment

Computed tomography (CT)/magnetic resonance imaging (MRI) scans will be performed and collected until confirmed disease progression is assessed by the Investigators according to RECIST v 1.1 or the start of new cancer therapy.

Radiographic images and physical findings (physical assessments) will be used by the Investigators for the local determination of disease progression and participant's treatment decisions.

For each participant, tumor response assessment will be performed by CT scan or MRI (if MRI is used, chest CT is mandatory) imaging of the chest/abdomen/pelvis (plus other regions as specifically required) and other established assessments of tumor burden if CT/MRI imaging is insufficient for the individual participant. All the scans performed at Baseline and other imaging performed as clinically required (other supportive imaging) need to be repeated at subsequent visits. In general, lesions detected at Baseline need to be followed using the same imaging methodology and preferably the same imaging equipment at subsequent tumor evaluation visits. Tumor assessments will be performed at Screening (up to 28 days before start of study intervention treatment for Part A and Part FE and up to 35 days before start of study intervention treatment for Part B), and then Q8W for 6 months. After 6 months, tumor assessments will be Q12W until PD or the end of the study.

For each participant, the Investigator will designate one or more of the following measures of tumor status to follow for determining response: CT or MRI images of primary and/or metastatic tumor masses, physical examination findings, and the results of other assessments. All available images collected during the study period will be considered. The most appropriate measures to evaluate the tumor status of a participant should be used. The measure(s) to be chosen for

sequential evaluation during the study must correspond to the measures used to document the progressive tumor status that qualifies the participant for enrollment. The tumor response assessment will be assessed and listed according to the Schedule of Activities (Table 1, Table 2, Table 3, and Table 4).

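### The missed-scan limits for PFS and DOR do not fit the switch from 8-week to 12-week scans: progression found after one missed scan counts if the last scan was Day 56 or Day 252, but is censored if it was Day 112 or Day 168

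*SAP*

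**What the plan says.** **Scan schedule.** For Parts A and FE the Protocol's Schedule of Activities (Section 1.3) sets scans "Then at D56, D112, D168 and then Q12W, until confirmed PD, the start of subsequent systemic anticancer therapy, or the end of the study". Part B has the same schedule: "At D56, D112, D168 and then Q12W, until confirmed PD, the start of subsequent systemic anticancer therapy, or the end of the study". Protocol Section 8.1.1.1 describes the switch as "After 6 months, tumor assessments will be Q12W until PD or the end of the study".

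**Censoring rule.** SAP Section 14.4 Table 7 picks the limit by the date of the last assessment. The short limit applies "If the last tumor assessment is within 6 months from the first dose", and the case is then censored at the last evaluable assessment for "Progression or death > 16 weeks after last tumor assessment". If the last assessment is later than 6 months, the censoring condition is "Progression or death > 24 weeks after last tumor assessment". Both limits are inclusive: an event at exactly 16 or 24 weeks still counts. Table 8, row 3, gives the censoring reason as "Event more than 16 (or 24 if beyond 6 months from the first dose of study treatment) weeks after last adequate post-baseline tumor assessment" and refers back to Table 7. SAP Section 14.2 applies the same censoring rules to DOR.

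**Conventions.** SAP Section 9.1 sets one month at 30.4375 days and takes time since an event as a plain difference of dates.

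**The concern.** A rule of this kind normally tolerates one missed scan and censors after two. The limits 16 and 24 weeks equal two 8-week and two 12-week intervals, so that appears to be the intent, although the SAP does not say so. The scan interval lengthens immediately after Day 168, but the longer limit applies only when the last scan is itself beyond 6 months. Scans on Days 112 and 168 therefore carry the 16-week limit although the next two intervals after them total 20 and 24 weeks. Two participants who each miss one scan and progress at the next can be handled in opposite ways.

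DOR is the more exposed endpoint. A confirmed response needs two determinations at least 4 weeks apart (SAP Section 14.1), so on scheduled scans the earliest confirmation is Day 112. A confirmed responder's last scan before progression is then normally Day 112 or later, which is where the mismatch begins. Missed efficacy evaluations are also foreseen: SAP Section 10.2 plans to count those due to COVID-19 and leaves the efficacy analyses unchanged.

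**Working it through.** **Inputs.** Scan days 56, 112, 168, then every 84 days: 252, 336, 420, 504 (Protocol 1.3). Limits 16 and 24 weeks, inclusive (SAP Table 7). Six months = 6 × 30.4375 = 182.6 days (SAP 9.1), so Day 168 is within 6 months and Day 252 is beyond. I take the last assessment to be the last adequate one before the event, as Table 8 words it.

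**Where the plan's limits appear to come from.** 2 × 8 = 16 weeks and 2 × 12 = 24 weeks. Each fits inside its own phase of the schedule.

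**Exactly one missed scan, progression at the next scheduled scan.** Gap in weeks = (day of the second scan after the last − day of the last scan) / 7.

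| Last scan | Progression found | Gap (weeks) | Table 7 limit | Result |
|---|---|---|---|---|
| Day 56 | Day 168 | 112/7 = 16 | 16 | event, exactly on the limit |
| Day 112 | Day 252 | 140/7 = 20 | 16 | censored at Day 112 |
| Day 168 | Day 336 | 168/7 = 24 | 16 | censored at Day 168 |
| Day 252 | Day 420 | 168/7 = 24 | 24 | event, exactly on the limit |

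**Other numbers of missed scans.** None missed: gaps of 8 or 12 weeks, always an event. Two missed: gaps of 28 to 36 weeks, always censored. Only the one-missed case varies.

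**Events on other days, with one scan missed.** The 16-week limit ends on Day 112 + 112 = Day 224, or Day 168 + 112 = Day 280. A death or an unscheduled progression is therefore censored from Day 225 to Day 252 after a Day 112 scan (more than 16 and up to 20 weeks), and from Day 281 to Day 336 after a Day 168 scan (more than 16 and up to 24 weeks). Earlier ones remain events.

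**Visit windows.** No window is stated for tumor scans as such. On-treatment visits carry ±2 days and long-term follow-up visits ±7 days (Protocol 1.3, Table 1).

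- Days 112 and 168: even with both scans moved by 7 days, the gaps are at least 140 − 14 = 126 days (18 weeks) and 168 − 14 = 154 days (22 weeks). Both stay above 16 weeks.
- Days 56 and 252: there is no slack. Taking whole-day offsets of −2 to +2 at each scan as equally likely (an assumption), 10 of 25 combinations exceed the limit and become censored.

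**Direction of the effect on the median.** Two illustrative cohorts of six, all events on scan days, with a Day 252 event recoded as censored at Day 112. When the curve sits at exactly 0.5, the midpoint convention is assumed.

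- Events at 56, 112, 168, 252, 336, 420. Survival is 0.5 from Day 168 to Day 252, so the median is (168 + 252)/2 = 210 days. After recoding, survival at Day 168 is 4/6 × 2/3 = 0.44 and the median is 168 days. It falls.
- Events at 56, 56, 252, 336, 336, 420. Survival is 0.5 from Day 252 to Day 336, so the median is 294 days. After recoding, survival stays at 4/6 until Day 336, then drops to 4/6 × 1/3 = 0.22, and the median is 336 days. It rises.

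Over all 252 patterns of the other five event times on the grid 56 to 420, equally weighted, the median rose in 57, fell in 36 and was unchanged in 159.

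**The case against.** The strongest reply is that the effect is narrow and visible. It needs a participant who is progression-free at Day 112 or Day 168, misses exactly one scan, has the event more than 16 weeks after the last scan, and has not started new therapy, which ranks higher in Table 8. Scans at end of treatment, at the 30-day safety visit and on suspicion of progression shorten many gaps. PFS and DOR are secondary with no formal hypothesis, OS is untouched, and each PFS censoring reason is tabulated and listed, so an affected participant can be found and recomputed. All of that stands. It limits the weight of the point but does not remove the inconsistency.

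Table 8 might also be thought to rescue the rule. Its row 3 does not say whether it is the scan or the event that lies beyond 6 months. If it were the event, the Day 112 and Day 168 cases (20 and 24 weeks against 24) would count. But Table 7 ties the limit explicitly to the last assessment and Table 8 defers to it, so Table 7 governs.

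Three stronger readings are tempting, and the documents do not support them:

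- That PFS and DOR are biased upward. Events are removed, but the risk set also shrinks, and a small-cohort median can move either way, as the examples show.
- That the outcome depends on which scan was missed rather than on how many. With none or two missed, the rule gives one answer throughout.
- That everything from 16 to 24 weeks after a Day 112 scan is wrongly censored. Beyond 20 weeks (Day 252) a second scan has been missed, and censoring is what a two-missed-scan rule would give.

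**Conclusion.** The point holds as a mismatch at the 8-to-12-week transition. With exactly one missed scan and progression at the next scheduled scan, Table 7 counts the event after Day 56 or Day 252 and censors it after Day 112 (20 weeks against 16) or Day 168 (24 weeks against 16). The affected ranges are more than 16 and up to 20 weeks after Day 112, and more than 16 and up to 24 weeks after Day 168. Plausible visit windows do not change this, and they make the two on-limit cases fragile.

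If a case occurs, one participant is 1/6 to 1/3 (17% to 33%) of a cohort of 3 to 6, and PFS and DOR are reported by dose level. How often it will occur and which way it would move the estimates are not established. The primary DLT and food-effect PK analyses are not affected. The result rests on scans falling at or near their scheduled days and on Table 7's last-assessment wording governing. That the limits were meant to allow one missed scan is an inference from their values.

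**What to change.** Before database lock, restate the rule in SAP Tables 7 and 8, and hence for DOR: censor only events that follow two or more consecutive missed or inadequate scheduled assessments. Equivalent limits, counted from the last adequate assessment:

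- Day 56, or treatment Day 1 if there is no post-baseline scan: 16 weeks
- Day 112: 20 weeks
- Day 168 or later: 24 weeks

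Add a stated tolerance for visit windows. With ±2 days at both scans the gap can run 2 + 2 = 4 days over nominal; with ±7 days in long-term follow-up it can run 7 + 7 = 14 days over. A one-week tolerance would therefore cover on-treatment scans but not follow-up scans.

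Use the same Day 1 limit in Table 7 footnote a, so that early deaths without an adequate baseline follow the same bound. Reword Table 8 row 3 so that the 6-month condition refers explicitly to the last assessment, as in Table 7.

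The cost is SAP wording and one derivation rule. No additional data or participant burden is involved.
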